#### 346 **9.4 Hierarchical Analyses**

347 To preserve the overall type 1 error for the primary and key secondary efficacy endpoints as  
348 defined in Section 6.1 and additional secondary efficacy endpoints listed in Section 6.2.1, a  
349 hierarchical testing procedure will be used. If the primary analysis for HbA1c results in a  
350 statistically significant result ( $p < 0.05$ ), then testing at the 0.05 level will proceed to the next  
351 outcome metric. This process continues iteratively moving to the next variable down on the list  
352 until a non-significant result is observed, or all 10 variables have been tested. If a non-  
353 significant result is encountered, then formal statistical hypothesis testing is terminated and any  
354 variables lower on the list will not be formally tested.  
355  
356 Regardless of the results of the hierarchical testing, summary statistics appropriate to the  
357 distribution will be tabulated by treatment group for each hierarchical outcome. A 95%  
358 confidence interval for the treatment group difference also will be calculated for all hierarchical  
359 outcomes listed above. However, a confidence interval that excludes zero will not be considered  
360 a statistically significant result if an outcome variable higher on the hierarchical list failed to  
361 reach statistical significance.

362 **9.5 Sensitivity Analyses**

- 363 • Covariate Adjustment: The primary analysis includes a pre-specified list of covariates. As  
364 an additional sensitivity analysis, any baseline demographic or clinical characteristics  
365 observed to be imbalanced between treatment groups will be added as covariates to the  
366 analyses of the primary endpoint. The determination of a meaningful baseline imbalance  
367 will be based on clinical judgment and not a p-value.
- 368 • Missing Data: All randomized participants will be included in the primary and key  
369 secondary analyses according to ITT and any missing data will be handled using direct  
370 likelihood. It is worth emphasizing that any statistical method for handling missing data  
371 makes a number of untestable assumptions. The goal will be to minimize the amount of  
372 missing data in this study so that results and conclusions will not be sensitive to which  
373 statistical method is used. To that end, the following methods will be performed:
  - 374 ○ Multiple imputation with a pattern mixture model assuming the dropout trajectory  
375 of the BP Group was that of the Control Group.
  - 376 ○ Available cases only.
- 377 • The primary analysis will be recalculated switching non-randomized participants  
378 assigned to the BP Group due to a protocol deviation to the Control group.

380 **9.6 Questionnaires and Other Outcomes Analyses**

381 Questionnaire scoring will be detailed in the Questionnaire Scoring Appendix.

382 Summary statistics of total and subscale scores appropriate to the distribution will be tabulated  
383 by visit and treatment group. For questionnaires administered to both randomization groups,  
384 comparisons will be made using similar linear models as described above for the primary and  
385 key secondary outcomes. If questionnaires include a total score, separate models will be run for  
386 the total score and any subscales, with the exception of the Clarke Hypoglycemia Awareness  
387 questionnaire. The models for comparing DTSQ scores between treatment groups will use a  
388 combined score calculated as the DTSQ-S score plus the DTSQ-C score. It will still adjust for  
389 the baseline DTSQ-S score.

390  
391 Similarly, for carbohydrate, total daily insulin, weight and BMI metrics, comparisons will be  
392 made using similar linear models as described above for the primary HbA1c analysis (Section  
393 9.1). Percentage change in the TDD of insulin over the first two-week period relative to the TDD  
394 of insulin in the last two-week period will not be tested because this metric is limited to BP  
395 group only. A 95% confidence interval will be reported for treatment group mean difference in  
396 total daily insulin, body weight, and body mass index.

397

398 **10. Safety Analyses**

399 All randomized participants will be included in the safety analyses and all of their post-  
400 randomization safety events will be reported. Separately, any adverse events occurring between  
401 screening and randomization will be reported.

402

403 All reportable adverse events will be tabulated by treatment group. Details will be provided in a  
404 listing of each event, including Medical Dictionary for Regulatory Activities (MedDRA) term  
405 and MedDRA System Organ Class. Safety analyses for the RCT will include events occurring  
406 on or after randomization until and including the 13-week visit, latest contact date, or Day 98  
407 from randomization, whichever occurs first. Analysis windows for the RCT and other periods are  
408 further detailed in Section 7.1.

409

410 Formal statistical testing only will be performed for selected safety endpoints. For the following  
411 outcomes, mean and standard deviation (SD) or summary statistics appropriate to the distribution  
412 will be tabulated by treatment group and formal statistical comparisons will be performed if there  
413 are enough events (at least 5 events combined between the BP aspart/lispro and Control Group):

- 414 • Number of SH events and SH event rate per 100 person-years
- 415 • Number of DKA events and DKA event rate per 100 person-years
- 416 • Other serious adverse events
- 417 • Worsening of HbA1c from baseline to 13 weeks by >0.5%

418

419 If enough events occur for the severe hypoglycemia (SH), DKA, and other serious adverse event  
420 (SAE) outcomes, the numbers of events will be compared between the two treatment groups  
421 during the RCT using a Poisson regression model adjusting for baseline age and HbA1c, and site  
422 as a random effect. For SH, the model will additionally control for whether or not the participant  
423 experienced at least 1 SH event prior to randomization. For DKA, the model will additionally  
424 control for whether or not the participant experienced at least 1 DKA event prior to  
425 randomization. If distribution is zero-inflated or the variance is greater than its mean, then a  
426 zero-inflated Poisson or negative binomial regression model will be considered. For worsening  
427 of HbA1c from baseline to 13 weeks by >0.5%, a logistic regression model adjusting for baseline  
428 age and HbA1c and site as a random effect will be used to compare the two treatment groups.

429

430 Since the Control Group is not provided with a study blood glucose meter or blood ketone meter,  
431 no treatment group comparisons of meter data will be performed. Additionally, no formal  
432 statistical comparison will be made of all reported adverse events combined since there are

433 specific requirements in the protocol for reporting certain events in real-time for the BP Group  
434 but not the Control Group, and adverse device effects are only reported for the BP Group.

435

436 No adjustments for multiple comparisons will be made for any safety analyses.

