5.1 Timing of Visits

876

The schedule for follow-up visits and phone contacts is the same for all treatment groups.

877

Phone contacts will occur after 1-2 days and after 7 (\pm 2) days.

878

Clinic visits will occur after 2 weeks (\pm 4 days), and then at 6 weeks (\pm 4 days), and 10 weeks (\pm 4 days) prior to the 13-week primary outcome visit (window 91-98 days from randomization).

880

In the event that in-person visits cannot be conducted due to institutional restrictions or the participant's unwillingness to attend an in-person clinic visit, visits may be conducted virtually via a Zoom, Skype, or similar video conference mechanism.

883

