5.2.2 Clinic Visits

891

The following procedures will be performed at each in-clinic visit, unless otherwise specified:

892

The date of the last menstrual period will be documented for female participants.

893

A urine pregnancy test will be performed for all women who are post-menarche, premenopausal and have not been surgically sterilized through the 10-week visit.

895

- If the visit is conducted virtually, a pregnancy test will be provided to the participant and verbal report of the result will be acceptable.*

897

Study staff will measure the participant's height and weight at 6 weeks and 13 weeks.

898

- If the visit is conducted virtually, a verbal report of the participant's weight and height will be acceptable. A scale will be provided for participants who do not already have a scale at home.*

901

- In the BP Group, if the weight has changed outside of $\pm 15\%$ of its current value, then the weight will be updated on the iLet GUI with the new value.*

903

Study staff will review any changes in the participant's medical history or medications to ensure continued eligibility, and any adverse events that may have occurred since their last study visit.

906

For the BP Group, recent CGM data (e.g. on the iLet's graph screen and/or in the summary statistics provided on the mobile app used by the study staff to download iLet data in the case of in-clinic study visits) will be reviewed and study staff may suggest a change to the permanent glucose target if indicated.

910 All study device data will be downloaded. In the BP Group, iLet data will be
911 downloaded to the Mobile App on the study tablet during each in-clinic visit. For
912 participants where in-clinic visits are not possible, iLet data may be downloaded at
913 select mid-study visits (e.g. at the 6-week visit or more often as needed) by either (1)
914 a study staff member visiting the participant or (2) shipping a study tablet to the
915 participant and guiding the participant through the data download process remotely.
916 For the final 13-week visit, participants who come to clinic will give back their iLet
917 and participants who are unable to come to clinic will factory-reset their iLet (which
918 will end their 13-week iLet treatment session but will not delete the data for the
919 treatment session from the iLet) and ship the iLet back to the study site. In all cases, a
920 final full data download will be performed.

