1674 Medical Dictionary for Regulatory Activities (MedDRA) term and MedDRA System Organ
1675 Class. Safety analyses for the RCT will include events occurring on or after randomization until
1676 and including the 13-week visit or Day 98 from randomization, whichever occurs first.

1677 Formal statistical testing only will be performed for selected safety endpoints. For the following
1678 outcomes, mean \pm SD or summary statistics appropriate to the distribution will be tabulated by
1679 treatment group and formal statistical comparisons will be performed if there are enough events
1680 (at least 5 events combined between the BP aspart/lispro and Control Group):

1681 Number of SH events and SH event rate per 100 person-years

1682 Number of DKA events and DKA event rate per 100 person-years

1683 Other serious adverse events

1684 Worsening of HbA1c from baseline to 13 weeks by >0.5%

1685 If enough events occur for the severe hypoglycemia and DKA outcomes and other serious
1686 adverse events, the numbers of events will be compared between the two treatment groups
1687 during the RCT using a robust Poisson regression as detailed in the SAP.

1688 Since the Control Group is not provided with a study blood glucose meter or blood ketone meter,
1689 no treatment group comparisons of meter data will be performed. Additionally, no formal
1690 statistical comparison will be made of all reported adverse events combined since there are

1691 specific requirements in the protocol for reporting certain events in real-time for the BP Group
1692 but not the Control Group, and adverse device effects are only reported for the BP Group.

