15    of an insulin-only configuration of the iLet Bionic Pancreas (BP) system versus a Control group  
16    using CGM during a 13-week study period.

17    The sample size is expected to include ~220 in the BP Group (using aspart/lispro) and ~110 in  
18    the Standard Care Control Group with 50% adults and 50% pediatric participants.

19    Following the initial screening visit, there will be the following visits:

20       a) Randomization Visit  
21       b) Day 1-2 Phone Call  
22       c) Week 1 Phone Call  
23       d) Week 2 Visit  
24       e) Week 6 Visit  
25       f) Week 10 Visit  
26       g) Week 13 Visit

27  
28    **4. Statistical Hypotheses**

29    The primary outcome is:

30       • Superiority in HbA1c at 13 weeks

32 Only the primary outcome needs to be met to declare device efficacy. The key secondary  
33 outcome is:

34 • Non-inferiority in CGM-measured time <54 mg/dL calculated over 13 weeks

35  
36 Primary and key secondary outcome analyses will combine pediatric and adult participants into a  
37 single analysis. The study hypotheses can be stated as follows:

38  
39 HbA1c Outcome:

40 • *Null Hypothesis:* There is no difference in the mean HbA1c at 13 weeks between BP  
41 aspart/lispro and Control Group  
42 • *Alternative Hypothesis:* There is a nonzero difference in the mean HbA1c at 13 weeks  
43 between BP aspart/lispro and Control Group

44  
45 Time <54 mg/dL Outcome:

46 • *Null Hypothesis:* There is a mean difference of at least 1% in the percentage of time spent  
47 with a sensor glucose level below 54 mg/dL between the BP aspart/lispro and Control  
48 Group over the 13 weeks  
49 • *Alternative Hypothesis:* There is a mean difference of less than 1% in the percentage of  
50 time spent with a sensor glucose level below 54 mg/dL between the BP aspart/lispro and  
51 Control Group over the 13 weeks

52  
53  
54 

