- 183 • RCT: Randomization Visit day to Week 13 visit day.

185 **7.2 CGM Metrics**

186 Baseline values for each CGM metric will be computed from either the participant's personal  
187 Dexcom G6 data or from the G6 wear prior to randomization. The most recent two weeks of  
188 CGM data prior to randomization will be included in the calculation of baseline CGM metrics.

189

190 If the subject has <168 hours of CGM data, then the baseline metrics will not be calculated and  
191 will be set to missing; this is not expected to occur as participants with <85% of CGM values  
192 during 14 days of CGM wear will need to complete a period of CGM wear to be eligible for  
193 randomization.

194

195 CGM metrics from the other periods will use all CGM data available. If a subject has <168  
196 hours of CGM data, then post-randomization CGM metrics will not be calculated and will be set  
197 to missing. The primary and secondary analyses utilize a direct likelihood model to account for  
198 missing CGM metrics data, as described in Section 9.

199

200 Percentage of CGM values that fall within a specified range will be calculated by dividing the  
201 number of CGM values that fall within the range by the total number of CGM readings.

202

203 A CGM-measured hypoglycemic event is defined as  $\geq 15$  consecutive minutes with a CGM  
204 glucose value  $<54$  mg/dL. The hypo event ends when there are  $\geq 15$  consecutive minutes with a  
205 CGM glucose value  $\geq 70$  mg/dL, at which point the participant becomes eligible for another hypo  
206 event.

207

208 Two separate definitions of CGM-measured hyperglycemic events will be calculated and  
209 assessed:

- 210 1)  $\geq 15$  consecutive minutes with a CGM glucose value  $>300$  mg/dL. The hyper event ends  
211 when there are  $\geq 15$  consecutive minutes with a CGM glucose value  $\leq 250$  mg/dL, at  
212 which point the participant becomes eligible for another hyper event.
- 213 2)  $\geq 90$  cumulative minutes with a CGM glucose value  $>300$  mg/dL within a 120-minute  
214 period. The hyperglycemia event ends when there are  $\geq 15$  consecutive minutes with a  
215 CGM glucose value  $\leq 180$  mg/dL, at which point the participant becomes eligible for  
216 another hyper event.

217

218 The amount of time with CGM data will be calculated as the number of CGM values multiplied  
219 by 5 minutes, with the exception that there can only be one value within a 5-minute period.

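### Do the differing end dates for the RCT safety window leave the severe hypoglycemia and DKA comparison undefined?

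*SAP*

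**What the plan says.** Three places set the end of the randomized-period safety window.

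- SAP Section 7.1 (Analysis Windows), in the safety list: "RCT: Randomization Visit day to Week 13 visit day". It gives no cap and no rule for a participant with no Week 13 visit.
- SAP Section 10 (Safety Analyses): "on or after randomization until and including the 13-week visit, latest contact date, or Day 98", with the earliest of these applying. It then says the windows are "further detailed in Section 7.1".
- Protocol Section 11.7 (Safety Analyses): "and including the 13-week visit or Day 98 from randomization, whichever occurs first". It has no last-contact limit.

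Protocol Section 5.1 schedules the follow-up visits "prior to the 13-week primary outcome visit (window 91-98 days from randomization", so Day 98 is the last day of the scheduled window. The SAP Section 7.1 visit table accepts Week 13 measurements from 14 days before to 28 days after Day 91.

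SAP Section 10 reports SH and DKA as rates per 100 person-years. If at least five events occur in the two arms combined, "the numbers of events will be compared between the two treatment groups" by Poisson regression, with a zero-inflated or negative binomial model as a fallback. Covariates are named. An offset and the end of person-time are not. Section 10 also says that every post-randomization safety event of randomized participants will be reported.

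**The concern.** SH and DKA are key safety outcomes in a trial meant to support a PMA application, and they are rare enough that one event can matter. Section 10 sends the reader to Section 7.1 for detail, and Section 7.1 lacks both of Section 10's limits. SAP Section 2 lists only the no-pooling change as a departure from the protocol, so the last-contact limit is an unlisted difference from Protocol Section 11.7.

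The texts disagree for two kinds of participant. One has the Week 13 visit after Day 98: an event between Day 99 and the visit counts under Section 7.1 but not under Section 10 or the protocol. The other has no Week 13 visit: Section 7.1 gives no end, Section 10 gives last contact, and the protocol gives Day 98. If analysts were truly free to choose, they could choose which events enter the comparison, what the rates are divided by, and, near five events, whether a test is run.

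**Working it through.** The documents state no person-time or event rate, so there is no figure to reproduce. The check applies each rule to cases and then sizes the differences.

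**1. Where the rules differ (end of window, in days)**

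| Case | SAP 7.1 | SAP 10 | Protocol 11.7 |
|---|---|---|---|
| Visit on Day 91 | 91 | 91 | 91 |
| Visit on Day 98 | 98 | 98 | 98 |
| Visit on Day 105 | 105 | 98 | 98 |
| Visit on Day 119 | 119 | 98 | 98 |
| No visit, last contact Day 49 | none | 49 | 98 |

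SAP 10 returns one answer in every row. It departs from the protocol only where contact ends early.

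**2. Late visits**

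The latest accepted measurement is Day 91 + 28 = 119, so at most 119 − 98 = 21 days are in dispute. The share of visits that are late (f) and the days late (d) are assumptions. Disputed share of person-time: s = fd / (98 + fd).

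- f = 2%, d = 3: 0.06 / 98.06 = 0.06%
- f = 10%, d = 7: 0.7 / 98.7 = 0.7%
- f = 20%, d = 21: 4.2 / 102.2 = 4.1%

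Given exactly five events, the chance that at least one falls in the disputed days is 1 − (1 − s)^5 = 0.3%, 3.5% and 19%. That is not the chance that the decision to test changes. The decision changes only if the full count reaches five and the count without the disputed days does not. With a Poisson total of mean m (an assumption), that chance is P(N ≥ 5; m) − P(N ≥ 5; m(1 − s)). It is largest at m of about 5, where it is 0.05%, 0.6% and 3.7%.

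**3. No Week 13 visit**

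SAP Section 3 expects about 330 participants ("The sample size is expected to include ~220 in the BP Group (using aspart/lispro) and ~110 in" Control). SAP Section 5 expects 200 + 100 = 300 to complete, leaving 30, or 9%. Let L be their mean day of last contact (an assumption), and put completers' visits at Day 98.

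- Person-time to last contact: 300 × 98 + 30L = 31,920, 30,870 and 29,820 days for L = 84, 49 and 14.
- Person-time to Day 98 for all: 330 × 98 = 32,340 days, larger by 1.3%, 4.8% and 8.5%.
- Rate for five events, 5 × 100 × 365.25 / days: 5.72, 5.92 and 6.12 to last contact, against 5.65 to Day 98.

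**4. Effect on the comparison between arms**

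Expected non-completers are 220 − 200 = 20 (BP) and 110 − 100 = 10 (Control). With equal L in both arms, the person-time ratio is (200 × 98 + 20L) / (100 × 98 + 10L) = 2 for any L. It is also 2 to Day 98 (220 × 98 / 110 × 98). The rate ratio is therefore the same under either rule.

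For a strongly unequal case, take L = 14 in BP and 84 in Control: (19,600 + 280) / (9,800 + 840) = 19,880 / 10,640 = 1.868. The rate ratio then differs between the rules by a factor of 2 / 1.868 = 1.07. With the timings reversed, (19,600 + 1,680) / (9,800 + 140) = 21,280 / 9,940 = 2.141, and the factor is 0.93.

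**The case for a change.** The strongest reply is that Section 10 cannot simply be declared the governing text, because it defers to Section 7.1, and the last-contact footnote in Section 7.1 belongs to the device-data table, not the safety list. Days between Day 98 and a late visit may still be days on the device, so dropping them loses some exposed time. A count model for people followed for different lengths of time needs an exposure term, and the SAP names none. Aligning the texts would take only a few lines, and the Fiasp SAP inherits the same wording because it takes its safety analyses from this SAP.

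The textual part of this stands: the cross-reference is untidy, the last-contact limit is not listed as a departure, and the offset is implied, not written. It does not follow that the analysis is open. The Section 7.1 line reads as naming the period, and Section 10 supplies the operative limits. The Day 98 cap is common to Section 10 and the protocol. Last contact hardly affects which events are counted, since events after last contact are seldom known. It mainly sets the denominator, and ending exposure when observation ends is standard practice. The SAP already does this for device data. A rate per 100 person-years over a stated window implies person-time over that window, and nothing in the SAP argues against the matching offset.

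**Conclusion.** The concern does not call for a change. The wording differs as described, but the gap is one that analysts fill sensibly: use the Section 10 window, end person-time on the same day, and use log person-time as the offset. Either cut, applied alike to both arms with matching person-time, gives a sound comparison, and no bias between arms is shown.

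The size is small. Scheduled visits are unaffected. Late visits dispute 0.06% to 4.1% of person-time and have at most a 0.05% to 3.7% chance of changing whether a test is run; the upper end requires one visit in five to be a full 21 days late. For non-completers, a five-event rate differs by 1.3% to 8.5%. The rate ratio is unchanged when dropout is proportionate and similarly timed, and it moves by about 7% even with very unequal timing, which is little for a ratio built on a handful of events. Lateness, timing of last contact and the Poisson total are assumptions, because the documents give none of them. All post-randomization events are reported whichever end date is used. Aligning the three texts would tidy a cross-reference but would not be expected to alter a conclusion.
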